Objectives: TAR-GET-1 (starting in 2019) is a multi-centre UK clinical trial that will compare standard of care (SOC) treatment of Acute Antibody-Mediated Rejection of the Kidney Transplant (AAMR) to standard of care plus rituximab (SOCR). This trial presents a rare opportunity to investigate the mechanisms of action of treatments (including rituximab) in AAMR. The rationale for using rituximab is the depletion of CD20-positive precursors to antibody-producing cells. However, rituximab has effects on other B cell subtypes and not all studies have shown antibody level reductions. Furthermore, AAMR is a heterogeneous disease, as defined by variability in mechanistic markers of AAMR in blood (B cell and antibody characteristics) and in transplant biopsies (histological features and gene expression). The objectives of this study are: 
• To investigate how treatment with rituximab affects these mechanistic markers, by comparing SOC to SOCR• To predict treatment benefit early, by analysing the effect of treatment on the mechanistic markers
Methodology: In patients enrolled in TAR:GET-1 (n=170), we will analyse mechanistic markers with established proof of concept (B cell and antibody characteristics, histological and transcriptional markers in the biopsy) at baseline and on follow-up, making use of clinical data, surplus diagnostic material from TAR:GET-1, and material from optional extra blood samples for research taken as part of TAR:GET-1, at 3,6 and 12 months. We will also offer an optional protocol biopsy at 6 months post treatment. Differences pre- and post-treatment will be analysed comparing SOC and SOCR. We will use mediation analysis models to decompose total effect of treatment effect on graft loss at 4 years (primary end point) into an indirect effect, which measures how much of the effect acts through the intermediate variable(s), and a residual direct effect.
Number of Subjects and Study populations: 170 subjects enrolled in TAR:GET-1
Outcome measures: same as primary outcome of TAR:GET-1 (graft loss at 4 years after initiation of treatment)
Inclusion Criteria: All patients enrolled in TAR:GET-1 Signed informed consent prior to any study specific procedures.

Exclusion Criteria:

None

Investigational Product: N/A**Duration of study:** 8 years (duration is dictated by the need for primary outcome of TAR-GET-1 to be reached)**Statistical Methods:**

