Data from this research project will be merged and linked with data from the TAR:GET-1 clinical trial by the statistician team.

Descriptive data

This will include description of all the biological characteristics analysed in 2 populations (rituximab + SOC and SOC) at baseline and at all follow-up time points. Summary statistics (mean, median, SD, range for continuous variables, and frequency tables for categorical variables) will be reported broken down by treatment, with exploratory figures (box-and-whisker plots for continuous, and stacked bar-charts for categorical).

Outcome analysis

Appropriate measures of differences between treatment groups will be estimated with point estimates, 95% confidence intervals, and p-values. Depending on the type of variable (continuous, categorical, time-to-event), regression techniques (linear, logistic, cox) and transformation of the endpoints will be considered.

Differences in characteristics comparing pre- to post-treatment samples at sequential time points will be analysed comparing the 2 groups of patients (SOCR versus SOC) using r mixed effect models repeat measurement techniques.

Mediation analysis, a special case of regression analysis, will be used to document that the treatment effects a change in the biomarker. We will use mediation analysis models to decompose total effect of treatment effect on graft loss into an indirect effect, which measures how much of the effect acts through the intermediate variable(s), and a residual direct effect. All the mediation analyses will be based on the Intention-to-Treat principle. We will fit the same form of outcome models as for the efficacy analyses, including the mediator as a covariate. We will use the mediation package within R which was developed specifically to make valid causal inference in explanatory analyses of the mechanisms of treatment-induced change in clinical outcomes in randomised clinical trials. All estimates of treatment differences will be summarised using effect size estimates and 95% confidence intervals (Dunn 2013). Collaborator for mediation analysis: [name], Professor of Statistical Methods for Medicine, UCL.

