2. STUDY OBJECTIVES

The primary objective is to investigate the mechanisms of treatments including rituximab in AAMR, by measuring the effect of SOCR versus SOC on mechanistic markers of AMR (B cell characteristics, antibody characteristics, end organ damage assessed by histology and transcript analysis)

The secondary objective is to predict treatment benefit early, by decomposing the effect of treatment on graft loss at 4 years (primary end point) into an indirect effect, which measures how much of the effect acts through the changes in mechanistic markers, and a residual direct effect.

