7. STATISTICS AND DATA ANALYSIS

The patient cohort size is dictated by TAR:GET-1: 170 patients, 85 in each arm. Under plausible modelling assumptions, for any biomarker that is on the mechanistic pathway between treatment and primary outcome, the power of the main study (90%) will be matched or exceeded when comparing the mean biomarker values between treatment groups. The mediation analysis will estimate for each biomarker the influence on allograft survival rate per unit change in biomarker, above and beyond, the direct effect of treatment. This will decompose the overall, marginal, treatment effect into a proportion attributable to a mechanism via the biomarker, and the complement attributable to direct effects, or other mechanisms. A similar multivariable analysis will proceed to estimate the mediation effects of multiple biomarkers acting in parallel, as an exploratory analysis using variable selection methods to control for over-fitting.

Data from this research project will be merged and linked with data from the TAR:GET-1 clinical trial by the statistician team.

Descriptive data

Mechanistic Evaluation of Treatments for Acute Antibody-Mediated Rejection of the Kidney Transplant (M.O.T. AMR) – Version 1.4 27/05/2020

This will include description of all the biological characteristics analysed in 2 populations (rituximab + SOC and SOC) at baseline and at all follow-up time points. Summary statistics (mean, median, SD, range for continuous variables, and frequency tables for categorical variables) will be reported broken down by treatment, with exploratory figures (box-and-whisker plots for continuous, and stacked bar-charts for categorical).

Outcome analysis

Appropriate measures of differences between treatment groups will be estimated with point estimates, 95% confidence intervals, and p-values. Depending on the type of variable (continuous, categorical, time-to-event), regression techniques (linear, logistic, cox) and transformation of the endpoints will be considered.

Differences in characteristics comparing pre- to post-treatment samples at sequential time points will be analysed comparing the 2 groups of patients (SOCR versus SOC) using mixed effect models repeat measurement techniques.

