Mediation analysis, a special case of regression analysis, will be used to document that the treatment effects a change in the biomarker. We will use mediation analysis models to decompose total effect of treatment effect on graft loss into an indirect effect, which measures how much of the effect acts through the intermediate variable(s), and a residual direct effect. All the mediation analyses will be based on the Intention-to-Treat principle. We will fit the same form of outcome models as for the efficacy analyses, including the mediator as a covariate. We will use the mediation package within R which was developed specifically to make valid causal inference in explanatory analyses of the mechanisms of treatment-induced change in clinical outcomes in randomised clinical trials. All estimates of treatment differences will be summarised using effect size estimates and 95% confidence intervals (Dunn 2013). Collaborator for mediation analysis: [name], Professor of Statistical Methods for Medicine, UCL

Data and all appropriate documentation will be stored for a minimum of 10 years after the completion of the study, including the follow-up period.

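### The mediation analysis promises a share of the overall effect on graft loss, but as written it yields a share of the effect among grafts still functioning when the marker is taken

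*Protocol*

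**What the plan says.** - **Target.** Section 7 of the protocol states: "This will decompose the overall, marginal, treatment effect into a proportion attributable to a mechanism via the biomarker". The remainder goes to a second part, which the same sentence describes in these words: "and the complement attributable to direct effects, or other mechanisms". The study summary has the same aim: "We will use mediation analysis models to decompose total effect of treatment effect on graft loss into an indirect effect". Section 2 makes it the secondary objective: "decomposing the effect of treatment on graft loss at 4 years (primary end point) into an indirect effect". There the mediators are changes in the markers, so a post-treatment value is needed.
- **Clock.** The summary defines the outcome as "graft loss at 4 years after initiation of treatment".
- **Model.** Section 7: "We will fit the same form of outcome models as for the efficacy analyses, including the mediator as a covariate". Also: "All the mediation analyses will be based on the Intention-to-Treat principle".
- **Several markers.** Section 7 also plans, as exploratory work, to "estimate the mediation effects of multiple biomarkers acting in parallel".
- **Schedule (section 3 and its visit table).** After baseline, serum DSA and BAFF are taken at months 3 and 12. B cell markers and blood transcriptomics are taken at months 3, 6 and 12. The optional protocol biopsy is at month 6 and is defined for patients with stable graft function. Leftover tissue from unscheduled indication biopsies, triggered by graft dysfunction, may also be used.

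**The concern.** The target covers all graft losses from the start of treatment. The mediator exists only for patients who reach a visit 3 or 6 months later. A marker cannot carry a treatment effect on a loss that happened before it was measured. Baseline samples cannot be mediators, and an indication biopsy before month 3 comes only from a selected group with failing function.

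In a model that simply adds the marker as a covariate, a patient with an earlier loss either has no value and leaves the model, or carries a value taken after the outcome. In the first case the patient leaves both the proportion and its complement, so the two no longer add up to the overall effect.

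A proportion mediated would be read as the part of the TAR:GET-1 effect that acts through a marker, and section 1.2 wants the project to inform surrogate markers. Proportions from a month-3 serum marker and a month-6 biopsy would also refer to different effects and could not be compared directly.

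**Working it through.** **The plan's own figure.** The only design figure is 90% power with 85 patients per arm. It cannot be reproduced, because no graft-loss rate, hazard ratio (HR) or significance level is given. With two-sided 0.05 assumed, 90% power needs, for example, four-year loss of 40% versus 17.7% (HR about 0.38) or 50% versus 26.1% (HR about 0.44). The point here does not depend on this figure.

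**Assumed inputs (none is in the protocol).** Four-year control loss L = 20%, 47% or 60%, with constant control hazard. Three treatment effects: HR 0.5 in year 1 then 0.8; constant HR 0.71; constant HR 0.4, which is nearer to the stated power.

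**Formula.** Control survival is S0(t) = (1−L)^(t/48), with t in months. S1(t) follows from the HR. Let D = S1(48) − S0(48) be the four-year risk difference and E = S1(t) − S0(t) the difference at the visit. The part of D arising before the visit can be ordered in two ways:

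- A = E × [S0(48)/S0(t)] / D
- B = E × [S1(48)/S1(t)] / D

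**Example: L = 47%, HR 0.5 then 0.8.** S0(48) = 0.530, S1(48) = 0.631, D = 0.101.

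- Month 3: S0 = 0.961, S1 = 0.980, E = 0.0193. A = 0.0193 × (0.530/0.961)/0.101 = 10.5%. B = 0.0193 × (0.631/0.980)/0.101 = 12.3%.
- Month 6: S0 = 0.924, S1 = 0.961, E = 0.0374. A = 21.2%, B = 24.3%.

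**Range over L and both orderings:**

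| Treatment effect | Before month 3 | Before month 6 |
|---|---|---|
| HR 0.5 then 0.8 | 10.1-12.7% | 20.6-25.0% |
| Constant HR 0.71 | 5.5-7.1% | 11.1-14.0% |
| Constant HR 0.4 | 4.8-8.0% | 9.7-15.7% |

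Overall this is about 5-13% at month 3 and 10-25% at month 6.

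**Effect on a reported proportion.** A proportion of 50% among grafts functioning at the visit is 50% × (1 − pre-visit part) of the whole effect. At month 3 that is 50% × (1 − 0.127) = 44% to 50% × (1 − 0.048) = 48%. At month 6 it is 38% to 45%. If there is no early loss, or no treatment effect on early loss, the two proportions agree.

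**Why month 3 is minor.** At L = 47% with HR 0.5 then 0.8, the large-sample Cox HR is 0.71 from time 0, 0.73 from month 3 and 0.75 from month 6. With 85 × (0.47 + 0.37), about 71 events, the approximate 95% interval is 0.71 × exp(±1.96 × 2/√71) = 0.45 to 1.13.

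**Front-loaded losses.** With a Weibull hazard of shape 0.5, replace t/48 by (t/48)^0.5. For control loss of 60% and HR 0.4 at month 3, (3/48)^0.5 = 0.25, so S0 = 0.4^0.25 = 0.795 and S1 = 0.4^0.10 = 0.912. With S0(48) = 0.400 and S1(48) = 0.4^0.4 = 0.693, E = 0.117 and D = 0.293, giving A = 20% and B = 30%. Over 30-60% control loss and HR 0.4-0.6, the range is 20-30% at month 3 and 29-42% at month 6.

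**The case against.** The strongest objection is that the handling of early losses belongs in a statistical analysis plan that is not shown. The protocol nowhere says that such patients are dropped, and a marker entered as a time-dependent covariate would keep them in the risk set. The complement in section 7, which includes other mechanisms, could also hold the effect on early losses. Both points stand in part. A reader might infer that the protocol discards early losses; the text does not say so. But the protocol does fix the target, the clock, the form of the model and the visit schedule, and no choice among the scheduled visits makes these fit together. Something must be added to the model or taken from the claim.

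A second objection is that the effect is small. For month 3 this is right, and every blood and serum marker has a month-3 sample. The protocol biopsy is optional, is expected in about half of patients, and the study does not depend on it.

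A third is that the size depends on the assumptions. This also stands: the HR 0.71 scenario would give only about 15-38% power at 85 per arm, well below the stated 90%, while front-loaded losses move the figures the other way.

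**Conclusion.** The point holds as a mislabelled result that should be corrected. Unless the plan says how earlier losses enter, the fitted proportion describes grafts functioning at the marker's visit. Under the assumed constant control hazard, the part of the effect left out is about 5-13% at month 3 and 10-25% at month 6. It is larger with front-loaded losses. The true size cannot be read from the protocol.

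Three stronger readings are tempting but not supported:

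- That close to half of the effect could be missed. Under the same constant-hazard assumptions this arises only for a month-12 mediator, and no section selects one.
- That nothing at all is collected before month 3. Baseline samples are scheduled and indication biopsies may come early; neither solves the problem.
- That the main comparison is in doubt. The comparison of marker levels between arms, which is the primary objective, is not touched. The point concerns the secondary objective, and mainly the month-6 biopsy.

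**What to change.** Keep the secondary objective. In section 7, and in the matching text of the study summary and section 2, do one of two things:

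- **(a)** State that each mediation result is the effect on graft loss after that marker's visit, among patients with a functioning graft then, analysed by randomised arm. Report losses before the visit by arm, as a separate part of the effect not attributable to the marker. Do not divide the resulting indirect effect by the full intention-to-treat effect.
- **(b)** Use a method that keeps losses before the visit in the model, and state that their effect is assigned to the complement.

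Under either option, state that the protocol-biopsy result applies to patients with stable function at month 6. Use one common post-treatment time point for the multi-biomarker model. No single post-treatment visit collects every marker, so this means month 3 without the protocol biopsy, or month 6 with the biopsy and the month-3 DSA and BAFF values.

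**Cost.** Only wording changes; no new samples or visits are needed. Option (a) has two downsides:

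- Events are lost. With constant hazard, the share of control losses before the visit is [1 − (1−L)^(t/48)]/L, which is 7-9% at month 3 and 14-18% at month 6 for L = 20-60%.
- The result is conditional on graft survival to the visit, so randomisation no longer fully protects it. With assumed unmeasured risk (gamma frailty, variance 0.5-1, HR 0.5, L = 20-60%), mean underlying risk among surviving patients in the rituximab arm exceeds that in the control arm by 0-5% at month 3 and 1-9% at month 6.

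Under option (b), the complement mixes direct effects with effects on losses before the visit, and the report should say so.

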1) Serum DSA characteristics at an extra timepoint (costs not covered in TAR:GET-1; 1 year), plus more detailed DSA analyses at all 3 timepoints including not only anti-HLA antibodies (IgG subtype, complement-activating ability) but also non-HLA antibodies;

2) Biopsy Banff histological scores (Roufosse 2018); The following data will be obtained for each biopsy:

- Total number of glomeruli
- Number of glomeruli with global sclerosis
- Number of glomeruli with segmental sclerosis
- Number of scorable glomeruli (excluding those with global/segmental sclerosis and ischaemic changes)
- Percentage of cortical scarring [tubular atrophy, interstitial fibrosis]

Mechanistic Evaluation of Treatments for Acute Antibody-Mediated Rejection of the Kidney Transplant (M.O.T. AMR) – Version 1.4 27/05/2020

- Full Banff lesion scores (t,i,ti,v,g,ptc,ct,ci,cg,cv,ah, C4d) and the microcirculation inflammation score (MI=g+ptc)
- Extent of peritubular capillary inflammation (% of cortex)
- Number of glomeruli with glomerulitis
- Number of glomeruli with capillary wall double contours
- Result of SV40 immunostain (positive/negative)
- Banff Classification for Allograft Pathology diagnostic category(ies) and subcategory(ies)
- Ultrastructural features: presence and distribution of electron dense deposits; extent of foot process effacement; extent of glomerular and peritubular capillary basement membrane multilayering; extent of ultrastructural endothelial activation; presence of tubuloreticular inclusions
- If performed, immunofluorescence staining pattern for IgG, IgA, IgM, C3, C1q, kappa light chain and lambda light chain;

3) Biopsy gene expression will be assessed using Nanostring nCounter technology (Adam 2016; Dominy 2019); this will include the AMR-gene expression signature (Haas 2018), and a B cell signature. As literature is evolving and it is possible to test for hundreds of genes on the same sample, the list of genes to be studied may evolve.

4) Serum BAFF (B cell activating factor) levels

Funding:

Part 1 (covered by Imperial BRC, Cambridge BRC and NIHR EME 129029): Shipping of the samples, 1), 2) and 3).

Part 2: 1) and 4); we will be applying to other funding sources, including Kidney Research UK and local NHS Trust research charity funds.

Optional samples covered by TAR:GET-1 consent process

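### The mediation remainder is read wholly as direct effects or other mechanisms, though on average part of it may be a mediated effect lost to marker measurement error

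*Protocol*

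**What the plan says.** The secondary objective (Protocol, Section 2) is to split the treatment effect on 4-year graft loss into "how much of the effect acts through the changes in mechanistic markers, and a residual direct effect".

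Section 7 says how. For each marker it will estimate "the influence on allograft survival rate per unit change in biomarker, above and beyond, the direct effect of treatment", and it assigns the rest of the treatment effect to "the complement attributable to direct effects, or other mechanisms". The model form is fixed: "We will fit the same form of outcome models as for the efficacy analyses, including the mediator as a covariate". The section relies on the R mediation package for causal validity. The Study Summary repeats the split into an indirect and a residual direct part.

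Reliability of the markers, assay error and biopsy-scoring error are not mentioned. Section 3 gives the number of readings:

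- **DSA:** baseline, 3 months and 1 year, so two readings after treatment.
- **Blood tubes:** offered at baseline, 3, 6 and 12 months, so up to three after treatment (the same subsection also speaks of three time points in all).
- **Biopsy:** one scheduled reading after treatment, the optional protocol biopsy at month 6. Indication biopsies are unscheduled.

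The protocol does not say how repeated readings enter the mediation model. The mixed models in Section 7 are planned for comparing markers between arms and are not linked to mediation.

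**The concern.** A measured marker is the true marker plus error. When it is used as an ordinary covariate, its slope on the outcome is pulled towards zero. Randomisation protects the effect of treatment on the marker, but not the slope of outcome on marker. The part of the indirect effect that is lost does not disappear: it reappears in the treatment coefficient, and the protocol's wording then calls it direct or due to another mechanism. Confidence intervals from the same model do not allow for this.

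Two conclusions are at stake. One is whether rituximab acts through the pathway being studied. The other is which marker deserves attention as a possible surrogate (Protocol, Section 1.2). If markers differ in precision, a more precisely measured one can show a larger mediated share than a noisier one that carries the same true effect.

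**Working it through.** **Inputs from the protocol.** Cohort: "The patient cohort size is dictated by TAR:GET-1: 170 patients, 85 in each arm". The marker enters as a plain covariate (Section 7). Readings are as listed above.

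**Inputs assumed.** Within-arm reliability L = variance of the true marker divided by variance of the measured marker, within arm. It is not stated, so 0.6 to 0.9 is used as a range. All outcome-model values below are also assumptions.

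**The plan's own figure.** Section 7 states that "the power of the main study (90%) will be matched or exceeded when comparing the mean biomarker values between treatment groups". This cannot be reproduced, because no alpha, graft-loss rates, effect size or marker SD are given. With two-sided alpha of 0.05 assumed, 85 per arm has 90% power at a standardised difference of (1.960 + 1.282) × √(2/85) = 0.497. The figure concerns marker means between arms and does not bear on the mediated share.

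**Attenuation.** Let a be the effect of treatment on the marker and b the marker slope given treatment. With classical error, a is unbiased and b becomes bL. If the effect is fully mediated (total = ab):

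- apparent indirect effect = abL
- apparent direct effect = ab(1 − L)
- apparent mediated share = L

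If the true share is s, the apparent share is sL. A true 50% becomes 45%, 40%, 35% and 30% at L = 0.9, 0.8, 0.7 and 0.6.

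**Repeated readings.** If k readings with independent errors are averaged, L becomes kL / (1 + (k − 1)L). Apparent mediated share when the truth is 100%:

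| L of one reading | one reading | mean of two | mean of three |
|---|---|---|---|
| 0.9 | 0.90 | 0.95 | 0.96 |
| 0.8 | 0.80 | 0.89 | 0.92 |
| 0.7 | 0.70 | 0.82 | 0.88 |
| 0.6 | 0.60 | 0.75 | 0.82 |

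**Check with binary graft loss.** The formula is exact only for a linear model, so a fully mediated effect was simulated with logistic graft loss (500,000 patients; treatment lowers the marker by 0.8 SD; log odds 1.2 per SD; total effect about −0.17 on the risk scale). The apparent share with one reading was 1.00 at L = 1, then 0.90, 0.81, 0.71 and 0.60 at L = 0.9 to 0.6. A Cox outcome model was not checked.

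**At the trial's size.** In 1,000 simulated trials of 170 with L = 0.7, the mean indirect effect was 0.1234 / 0.1724 = 72% of the mean total effect. The average spurious direct effect was 0.1724 − 0.1234 = 0.049, against a sampling SD of about 0.07. The mediated share fell below 1 in 77% of trials, compared with 53% when there was no error.

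**With marker-outcome confounding.** Adding an assumed unmeasured confounder to the same fully mediated effect gave apparent shares of 1.30, 1.17, 1.06, 0.92 and 0.79 at L = 1, 0.9, 0.8, 0.7 and 0.6. Error still lowers the share, but the net bias can go either way.

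**Where planned data can inform L.** Section 3 records "Number of glomeruli with glomerulitis" and "Number of scorable glomeruli (excluding those with global/segmental sclerosis and ischaemic changes" in each biopsy. If the inflamed fraction were the mediator, with mean p = 0.3 and true between-patient SD s = 0.20 (both assumed), sampling alone gives L = s² / (s² + (p(1 − p) − s²)/n) = 0.04 / (0.04 + 0.17/n). That is 0.62, 0.70, 0.78 and 0.82 for n = 7, 10, 15 and 20 glomeruli. It does not apply to graded Banff scores.

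**The case against.** The strongest reply is that the quoted words define a target, not an estimate. Splitting a total effect into the part through a marker and the rest is the usual definition of indirect and direct effects. Attenuation is a property of the estimator, and its correction is commonly left to an SAP, which is not shown here. This stands in part: the lack of a named correction method is not a finding. However, the protocol fixes both the estimator and the meaning of its remainder, and offers no other reading of the estimated value.

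A second reply also stands. For predicting benefit early, the measured marker is what a user would have, so the uncorrected estimate is relevant in its own right.

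A reader might infer more than the documents support:

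- **That every mediator is a single reading.** This fits only the scheduled month-6 biopsy. DSA has two readings after treatment and blood markers up to three.
- **That the bias always understates mediation.** That requires classical, non-differential error and no marker-outcome confounding. Only treatment is randomised. With several correlated markers in one model, error can also shift effect between markers.
- **That this trial would report a false direct effect.** At 170 patients the average spurious effect is smaller than its sampling SD.
- **That serum markers will outrank biopsy markers.** The protocol gives no reliability for either.
- **That within-patient variance from the mixed models bounds the error.** Over 3 to 12 months it includes true change, and it misses errors that persist across visits.

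**Conclusion.** The point holds as one of interpretation. Read as Sections 2 and 7 direct, the remainder can include mediated effect lost to marker error, which is neither a direct effect nor a mechanism. Under the stated error model and without confounding, the average misattributed part of a fully mediated effect is about 1 − L. That is 10% to 40% for one reading at L = 0.9 to 0.6, and less where readings are averaged (18% for two and about 13% for three at L = 0.7). Each figure depends on an assumed L, so none is a prediction for this trial. The bias is systematic and the planned intervals do not cover it, but at this sample size it does not dominate sampling error. This is a cheap improvement and does not invalidate the analysis.

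**What to change.** In Sections 2 and 7, and in the matching Study Summary text, describe the remainder as *effect not captured by the measured marker (direct effects, other mechanisms and marker measurement error)*.

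Keep the uncorrected indirect effect as the main estimate. Beside it, add a sensitivity analysis over a stated reliability range, for example 0.6 to 0.9; the choice of correction method can sit in the SAP. Use the recorded glomerular counts to inform sampling error only if a glomerular fraction is the mediator. Do not treat within-patient variance over 3 to 12 months as a firm bound on error. When mediated shares are compared across markers, say that differences may partly reflect precision.

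The cost is a change of wording, modest extra analysis on data already planned, and wider intervals for the corrected estimates. No further patients or samples are needed.

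### The marker comparison between arms is worded as a pre-to-post difference with no baseline adjustment, while the 90% power is stated for mean values; adjusting for baseline would be at least as precise and needs no new data

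*Protocol*

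**What the plan says.** The primary objective (section 2) is the effect of SOCR versus SOC on mechanistic markers. The protocol words the comparison as a pre-to-post difference in three places:

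- Study Summary, Methodology: "Differences pre- and post-treatment will be analysed comparing SOC and SOCR".
- Section 7, Outcome analysis: "Differences in characteristics comparing pre- to post-treatment samples at sequential time points will be analysed comparing the 2 groups of patients (SOCR versus SOC"), to be done "using mixed effect models repeat measurement techniques".
- Study Summary, Statistical Methods: the same sentence, nearly word for word.

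None of these says what role the baseline value plays in the model.

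The power statement opens section 7. The cohort size is inherited: "The patient cohort size is dictated by TAR:GET-1: 170 patients, 85 in each arm". Then, "Under plausible modelling assumptions, for any biomarker that is on the mechanistic pathway between treatment and primary outcome", it is claimed that "the power of the main study (90%) will be matched or exceeded when comparing the mean biomarker values between treatment groups". No marker effect size, SD, correlation or alpha is given.

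Section 7 also says, for treatment-group differences in general, that "regression techniques (linear, logistic, cox) and transformation of the endpoints will be considered".

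**The concern.** Within one section, power is claimed for one contrast (mean values between arms) and the analysis is described as another (differences from baseline between arms). The two have different variances, so the claim for the first does not carry over to the second.

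The wording also leaves room for the least efficient use of the baseline. In a mixed model where baseline is one of the repeated responses and each arm has its own baseline mean, the arm-by-time contrast with complete data is exactly the difference in mean change. For biopsy markers this reading comes naturally. The visit table in section 3 schedules one baseline biopsy and one later protocol biopsy, so a repeated-measures analysis of the scheduled biopsies has nothing repeated unless baseline is itself a response.

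At stake is precision in the analysis that answers the primary objective. Baseline values are taken anyway, and using them as a covariate is never less precise than subtracting them, apart from the trivial cost of estimating one slope.

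**Working it through.** **Inputs from the protocol.** 85 per arm, and power of at least 90% for mean marker values (both section 7).

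**Assumptions, not in the protocol.** Continuous marker, complete data, two-sided alpha 0.05, normal approximation, equal SD at baseline and follow-up, and a range of correlations r.

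**The plan's own figure.** The 90% cannot be reproduced, because none of its inputs is given. It can only be calibrated. With follow-up means alone and 85 per arm, power is exactly 90% when

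delta/SD = (1.960 + 1.282) × sqrt(2/85) = 0.497.

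**Variance of each contrast**, in units of 2·SD²/85:

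- follow-up means only: 1
- unadjusted change: 2(1 − r)
- follow-up adjusted for baseline: 1 − r²

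The ratio of change to adjusted is 2(1 − r)/(1 − r²) = 2/(1 + r), which is never below 1.

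**Worked example, r = 0.3.**

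- Change: 3.242/sqrt(1.4) = 2.740; 2.740 − 1.960 = 0.780; power 78.2%.
- Adjusted: 3.242/sqrt(0.91) = 3.398; 3.398 − 1.960 = 1.438; power 92.5%.

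**Range of r, at delta/SD = 0.497:**

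| r | Change | Adjusted | Variance ratio |
|---|---|---|---|
| 0.1 | 67.6% | 90.3% | 1.82 |
| 0.3 | 78.2% | 92.5% | 1.54 |
| 0.5 | 90.0% | 96.3% | 1.33 |
| 0.7 | 98.7% | 99.5% | 1.18 |

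**Simulation check.** With 8,000 trials at r = 0.3, the standard errors were 0.154 (follow-up only), 0.182 (change) and 0.147 (adjusted). The formulas give 0.153, 0.181 and 0.146. A model of change that includes baseline as a covariate gave the same treatment estimate as the adjusted follow-up analysis in every trial.

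**Sensitivity to the two calibrating assumptions.**

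- Power on follow-up means: if it is really 95%, 97% or 99%, unadjusted change keeps 90% down to r of about 0.38, 0.30 or 0.13.
- Equal SDs: with baseline SD s0 and follow-up SD s1, change beats follow-up means alone only when r > s0/(2·s1). For s1/s0 of 0.75, 1.5 or 2, that break-even is 0.67, 0.33 or 0.25.
- Adjustment against change with unequal SDs: the variance difference is (s0² + s1² − 2r·s0·s1) − s1²(1 − r²) = (s0 − r·s1)², which is never negative. The preference for adjustment therefore does not depend on r or on equal SDs. Only the size of the gain does.

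**The case against.** The strongest reply is that the protocol fixes no unadjusted change score. It names a mixed model and stops. A model with baseline as a covariate, or with one common baseline mean for both arms, fits the same words and loses nothing. That choice is often left to the analysis plan, which is not shown. This stands, and it is why the point is a recommended clarification and not a demonstrated error.

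A second reply is that section 7 separately provides regression for treatment-group differences, which matches the power statement, and that the pre-to-post analysis is additional. This stands in part. Baseline is neither included nor excluded there, and the summary's account of the methodology mentions only the pre-to-post comparison.

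A reader might go further and infer that power falls below 90% whenever r is under 0.5. The documents do not support that. The 90% is a floor, limited to markers on the causal pathway, under assumptions that are not listed. The 0.5 threshold needs exactly 90% on follow-up means and equal SDs.

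Nor do the documents show that r is low. One can argue that entry on biopsy-proven disease narrows the baseline range. However, the protocol itself stresses variability between patients in these same markers (Study Summary; section 1.1), and it reports no correlation for any of them.

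Finally, the 85-per-arm illustration does not describe every marker. Protocol biopsies and fresh B-cell samples are each expected from about 50% of patients, and Banff lesion scores are graded. For continuous markers the variance ratio holds at any sample size, but the power figures do not. For graded scores the ratio is only a guide.

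**Conclusion.** The point holds as a mismatch and a missed improvement. The comparison that is described (difference from baseline) is not the one for which power is claimed (mean values), and no baseline adjustment is stated.

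If baseline is handled as an ordinary visit with free arm means, the variance is 2/(1 + r) times what adjustment would give. Under the stated assumptions, power at r = 0.3 would be about 78% instead of 92%. By r = 0.7 the difference is under 2 percentage points. If the analysts already intend adjustment or a common baseline mean, nothing is lost and only the wording needs repair. The actual shortfall cannot be determined from the protocol.

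**What to change.** In section 7 and in the Study Summary, state that continuous markers are compared between arms at each marker's own scheduled post-treatment visits, following the visit table in section 3:

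- serum DSA and BAFF at months 3 and 12;
- protocol biopsy markers at month 6;
- B-cell and blood transcriptomic markers at months 3, 6 and 12.

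The model is for post-treatment values adjusted for the baseline value, with a baseline-by-visit term where there is more than one visit. A longitudinal model with the two arms' baseline means constrained equal serves the same purpose. It also keeps patients who lack a baseline value, which matters for the optional blood tubes.

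Keep change from baseline as description. Reword the power statement so that it refers to this contrast, and list the effect size, SD, correlation and alpha behind it.

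The cost is a few sentences. No new samples are needed: section 3 expects enrolment biopsy material and DSA serum from every patient, and baseline blood tubes are already offered. Settling this before marker data are compared by arm also removes any later choice between change and adjusted results.
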